9. BIOMARKER STUDIES

Patients will be asked for permission to obtain and store either a tumor tissue block from previous biopsy and/or undergo sequential biopsies. Patients who do not have archival tumor tissue will be asked to provide a fresh pre-treatment tumor biopsy. All patients will have tumor tissue collected (40 unstained slides or one tumor block) if deemed safe and feasible at baseline, on treatment and post-treatment. A vial of EDTA blood will also be obtained. All patients consented to Dana-Farber Cancer Institute Protocol# 11-104 will undergo Oncopanel testing which analyzes 300 cancer relevant genes. Paired tumor specimens will be analyzed for genotyping utilizing next-generation sequencing techniques and receptor phospho-tyrosine kinase activity utilizing kinome assays according to already established methods. We will evaluate tumor *RET* and *RAS* mutation status, and phospho-tyrosine kinase activity, and correlate with outcomes.

Whole exome sequencing will be performed on tumor and normal genomic DNA on all responders.

Whole-exome sequencing is a diagnostic test for patients with nonspecific or unusual disease presentations of possible genetic cause and for patients with clinical diagnoses of different and unrelated genetic conditions. The purpose is also to study how DNA, genes, proteins, and other molecules in the tumor may affect response to treatment. Whole exome sequencing will be performed/coordinated at Broad Institute. The goal is to obtain 100-500ng of genomic DNA from FFPE blocks. To obtain sufficient amount of DNA, we need one of the following:

- a) 5-10 unstained 10 micron FFPE slides (10 ideal)
- b) 2-3 30 micron scrolls (3 ideal)
- c) 2 x 1mm cores or equivalent (3 x 0.6mm cores, 1 x 2mm core, etc)

In addition, one tube of whole blood (frozen at -80° C or fresh) needed for isolation of normal blood.

Protocol for sending biological sample (blood or fresh tissue biopsy)

- 1. Samples will be stored a -80°C the day of collection. They can be stored together.
- 2. During the first week of each month, biological samples will be sent on dry ice to:

Protocol for sending archival tissue sample collection
When the archival tissue samples are available, one block will be shipped ambient to:

10. STUDY CALENDAR

Screening evaluations are to be conducted within 3 weeks prior to study registration. Scans and x-rays must be done \leq 4 weeks prior to study registration. In the event that the participant's condition is deteriorating, laboratory evaluations should be repeated within 48 hours prior to initiation of the next cycle of therapy.

Procedures	Screening	Treatment Cycle 1 Day 1 of			Treatment Cycle 2 Day 1 of		Treatment Cycle 3 and beyond Day 1 of	End Of Treatment	Follow up until first progression	After first progression. Follow up by phone until death ⁱ
			Week 2	Week 3	Week 1	Week 3	Week 1			
Clinic Visit	X	X	X	X	X	X	X			
Informed consent	X									
Demographics	X									
Medical history	X									
Concurrent meds	X	X	X	X	X	X	X	X		
Physical exam	X	X	X	X	X	X	X	X		
Vital signs	X	X	X	X	X	X	X	X		
Height	X									
Weight	X	X	X	X	X	X	X	X		
Performance status	X	X	X	X	X	X	X	X		
CBC w/diff, plts	X	X	X	X	X	X	X	X		
Serum chemistry ^a	X	X	X	X	X	X	X	X		
B-HCG ^b	X	X			X		X	X		
Urinalysis ^k	X	X	X	X	X	X	X	X		
UPCR ⁿ	X									
EKG	X	X						X		
CT/MRI/PET ^d	X	Xc						Xe	Xf	
Archival or fresh tumor biopsy	X			χm				Xm		
Tumor measurements	X						Xc	Xe	Xf	

Tumor markers ^g	X	X			X		X	X		
QOL questionnaire ^h		χl		X	X	X	X	X	X	
Regorafinib		Once d	Once daily, weeks 1-3 in each cycle							
Adverse Events ^j			X							

- a) Albumin, alkaline phosphatase, total bilirubin, bicarbonate, BUN, calcium, chloride, creatinine, glucose, LDH, phosphorus, potassium, total protein, SGOT [AST], SGPT [ALT], sodium, INR, PT and PTT.
- b) Serum pregnancy test (women of childbearing potential). b-HGG testing for women of childbearing potential should be done prior to the initiation of each cycle.
- c) Every 8 weeks until first progression, death, or 24 months from study registration whichever occurs first (also obtain a survival status update at each visit).
- d) The same imaging modality should be used throughout the study.
- e) In subjects who discontinue study therapy without confirmed disease progression, a tumor assessment should be performed at end of treatment (i.e. date of discontinuation +/- 4 week window). If a previous scan was obtained within 4 weeks prior to end of treatment date then a scan at end of treatment is not mandatory.
- f) Post end of protocol treatment, if first progression has not yet been confirmed, tumor assessments are to continue every 2 months (+/- 7 days) until first progression, start of new cancer treatment regimen, death, or 24 months from study registration, whichever occurs first.
- g) Serum calcitonin, carcinoembryonic antigen (CEA), CA 19-9 for MTC, Thyroglobulin, TSH and free T4 in DTC.
- h) MD Anderson Symptom Inventory Thyroid (MDASI-Thy)
- i) After first progression, participants will be followed by phone only, every 3 months (+/- 2 weeks) for 24 months from study registration or until death whichever occurs first.
- j) Patients will be assessed monthly for adverse events; until first disease progression.
- k) Full urinalysis (dipstick plus microscopic evaluation) at the Screening and End-of-Treatment visits and a basic urinalysis (dipstick only) at each visit indicated prior to administration of trial drug. If the basic urinalysis is abnormal, then a full urinalysis should be performed.
- 1) Patient needs to complete this timepoint prior to starting protocol therapy.
- m) For patients with accessible tumors. Optional but strongly encouraged.
- n) Patients with persistent proteinuria \geq Grade 3 NCI-CTCAE v4.0 are excluded.

Assessments must be performed prior to study registration. Study assessments and agent should be administered within ± 3 days of the protocol-specified date, unless otherwise noted. Biological Sample Collection:

Sample Type	Screening	1 2	End of Treatment
		Week 3	
Blood (whole blood with EDTA)	X	X	X
Archived tumor	X		
Fresh Biopsy	Xa	Xb	Xb

- a) Fresh screening biopsy required for patients without sufficient archival tumor tissue.
- b) For patients with accessible tumors. Optional but strongly encouraged.
- c) For participating sites that are not Dana-Farber Cancer Institute, fresh biopsy and blood will be stored at -80°C until they can be sent to Dana-Farber Cancer Institute.

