5. TREATMENT PLAN

5.1 Treatment Regimen

Regorafenib will be administered as monotherapy during the study. Subjects will take one dose daily for 3 weeks on /1 week off. One cycle is 28 days.

During cycle 1, patients will start taking 80mg for one week. If no significant drug related toxicities (SDRT's) occur, the dose will be escalated to 120mg daily starting day8. If no SCRT's occur, the dose will be escalated to 160mg daily.

From cycle 2 onward, the highest tolerated dose will be the treatment dose level.

Dose Escalation Plan:

Cycle	Week	Daily Dose	
Cycle 1	Week 1	80 mg	Two 40-mg tablets of regorafenib
	Week 2	120 mg	Three 40-mg tablets of regorafenib
	Week 3	160 mg	Four 40-mg tablets of regorafenib
	Week 4	No dosing	
Cycle 2-onwards	Week 1-3	Highest tolerated dose	
	Week 4	No dosing	

Regorafenib tablets should be taken once a day with approximately 8 fluid ounces (240 mL) of water after a low-fat (<30% fat) meal. Some examples of lowfat meals are:

- Two slices of white toast with 1 tablespoon of low-fat margarine and 1 tablespoon of jelly and 8 ounces (240 mL) of skim milk (approximately 319 calories and 8.2 g of fat).
- One cup of cereal (i.e. Special K), 8 ounces (240 mL) of skim milk, one piece of toast with jam (no butter or marmalade), apple juice, and one cup of coffee or tea (2 g fat, 17 g protein, 93 g of carbohydrate, 520 calories.

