5.8 Criteria for Taking a Participant Off Protocol Therapy

Duration of therapy will depend on individual response, evidence of disease progression and tolerance. Treatment must discontinue regorafenib if any of the following criteria are met:

Disease progression by clinical evaluation or as documented by RECIST v 1.1.

- Intercurrent illness that prevents further administration of treatment
- Unacceptable adverse event(s)
- Drug is held for 28 days or longer
- Participant demonstrates an inability or unwillingness to comply with the oral medication regimen and/or documentation requirements
- Participant decides to withdraw from the protocol therapy
- General or specific changes in the participant's condition render the participant unacceptable for further treatment in the judgment of the treating investigator

Participants will be removed from the protocol therapy when any of these criteria apply. The reason for removal from protocol therapy, and the date the participant was removed, must be documented in the case report form (CRF). Alternative care options will be discussed with the participant.

A QACT Treatment Ended will be filled out when a participant is removed from protocol therapy. This form can be found on the QACT website or obtained from the QACT registration staff.

In the event of unusual or life-threatening complications, treating investigators must immediately notify the Overall PI, [name]

5.9 **Duration of Follow Up**

Participants will be followed through scans and visits until first progression or start of new cancer treatment regimen. Participants will be followed for survival for two years from study entry or until death-whichever occurs first.

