5.10 Criteria for Taking a Participant Off Study

Participants will be removed from study when any of the following criteria apply:

- Lost to follow-up
- Withdrawal of consent for data submission
- Disease Progression by clinical evaluation or as documented by RECIST v1.1
- Death

The reason for taking a participant off study, and the date the participant was removed, must be documented in the case report form (CRF).

A QACT Off Study Form will be filled out when a participant comes off study. This form can be found on the QACT website or obtained from the QACT registration staff.

For Centralized Subject Registrations, the research team submits a completed Off Treatment/Off Study form to ODQ when a participant comes off study. This form can be found on the ODQ website or obtained from the ODQ registration staff.

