7.4 Safety

All subjects who receive at least one dose of study treatment will be valid for the safety analysis. All observations pertinent to the safety of the study treatment will be recorded and included in the final report.

Safety variables include the following: AEs, laboratory changes (complete blood counts, electrolytes, chemistry, and coagulation), changes in vital signs (blood pressure, heart rate, respiratory rate, and temperature) and ECG and, in some instances, changes in chest x-ray images, as produced at the investigator's discretion (e.g., for evaluation for pneumonia).

All AEs whether considered drug-related or not, will be reported in with a diagnosis, start/stop dates, action taken, whether treatment was discontinued, any corrective measures taken, outcome, and other possible causes. For all events, the relationship to treatment and the intensity of the event will be determined by the investigator.

This trial will use the NCI-CTCAE v4.0 criteria for assessment of toxicity and SAE reporting with regard to toxicity grade.

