The expectedness of AEs will be determined by Bayer according to the applicable reference document and according to all local regulations. As with any new chemical entity, there is always potential for unexpected adverse events, including hypersensitivity reactions.

Based on data studies with regorafenib and from current knowledge of the pharmacological properties

of other small molecule tyrosine kinase inhibitors in this drug class, as soon as there is reasonable suspicion of any of the following AEs, the investigator should immediately notify the sponsor as outlined in Section 7.6.3.8.

7.6.3.10 **Reportable adverse events include:**

- Acute renal failure (NCI-CTCAE version 4.0 2: grade 3) or severe proteinuria (NCI- CTCAE version 4.0 2: grade 3)
- Interstitial lung disease
- Acute cardiac failure
- Clinically significant bleeding (NCI-CTCAE version 4.0 2: grade 3)
- Stevens-Johnson Syndrome and erythema multiforme
- Hepatic failure
- Reversible posterior leukoencephalopathy syndrome
- Gastrointestinal perforation or fistula

7.6.3.11 **Pregnancies**

The investigator must report to Bayer any pregnancy occurring in a study subject, or in his partner, during the subject's participation in this study. The report should be submitted within the same timelines as an SAE, although a pregnancy per se is not considered an SAE.

For a study subject, the outcome of the pregnancy should be followed up carefully, and any abnormal outcome of the mother or the child should be reported.

For the pregnancy of a study subject's partner, all efforts should be made to obtain similar information on course and outcome, subject to the partner's consent.

For all reports, the forms provided are to be used.

7.6.3.12 **Progressive disease**

If progressive disease leads to signs and symptoms that meet the criteria for an SAE (i.e., hospitalization, disability, death, or important medical event), the signs and symptoms should be reported as an SAE and not the underlying progressive disease.

7.6.3.13 **Death**

If any subject dies during the trial or within 30 days of the end-of-treatment visit, the investigator will inform Bayer and record the cause of death in detail (using the SAE Form) within 24 hours.

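### Routine adverse-event assessment ends at first progression, so the safety observation period depends on the efficacy outcome and new non-fatal events have no fixed post-treatment window

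*Combined protocol and SAP*

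**What the plan says.** The rule for routine collection is footnote j of the study calendar: "Patients will be assessed monthly for adverse events; until first disease progression".

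Several other provisions bear on it:

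- Section 5.8 makes this a reason to stop treatment: "Disease progression by clinical evaluation or as documented by RECIST v 1.1". Section 5.10 lists the same event as a reason to leave the study: "Disease Progression by clinical evaluation or as documented by RECIST v1.1".
- Footnote i describes contact afterwards: "After first progression, participants will be followed by phone only, every 3 months (+/- 2 weeks) for 24 months from study registration". It mentions no adverse-event collection.
- Section 5.9 ends follow-up by scans and visits at first progression or at the start of a new cancer regimen. Footnote f puts the same two limits, with death and 24 months from registration, on tumour assessments after treatment.
- Section 7.4 makes everyone with at least one dose part of the safety analysis and promises: "All observations pertinent to the safety of the study treatment will be recorded and included in the final report".
- Section 7.6.3.8 follows each serious adverse event to resolution or stabilization.
- Section 7.6.3.13 requires a report to the drug supplier in this case: "If any subject dies during the trial or within 30 days of the end-of-treatment visit".
- Section 7.6.1 opens the adverse-event period at informed consent. It gives no closing date.
- Section 13 says that adverse events will be graded by CTCAE and their frequencies summarised. It names no analysis window, no treatment-emergent definition and no adjustment for observation time.

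**The concern.** An adverse-event frequency can be interpreted only if the reader knows over what period each patient was observed. Here the period closes on an efficacy event. Where that event is also the reason for stopping the drug, it closes at about the time treatment ends. Late treatment-related events are then least likely to be recorded in patients who progress. Patients who stop without progressing can accumulate events long after the drug has gone, including events on a later therapy.

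Safety and tolerability is the first secondary objective (1.3). The DTC cohort uses a stepwise dosing schedule that section 2.3.2 says was tested to ameliorate side effects. The tolerability figures are therefore likely to be quoted and compared with other series, which usually requires a stated collection window.

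**Working it through.** The plan states no figure for this point, so there is nothing to reproduce. The check sets the provisions side by side and adds three small calculations.

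**Step 1. When does collection of new events close?**

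| Reason for stopping | Routine assessment (footnote j) | New non-fatal events after the last dose | Deaths |
|---|---|---|---|
| Progression | Closes at progression | Only what the end-of-treatment visit captures | To 30 days after the end-of-treatment visit |
| Toxicity or other reason, no new therapy | Monthly until progression | Collected monthly | Same |
| Toxicity or other reason, then a new therapy before progression | Still open, as footnote j is worded | Collected as worded, although 5.9 has ended visits | Same |

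The 7.6.3.8 rule follows up serious events once they are known. It sets no period for detecting new ones. The 7.6.3.13 rule covers fatal events only. Neither supplies the missing window for new non-fatal events in the first row.

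**Step 2. Do the closing rules agree?** They do not:

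- Footnote j stops at progression only. Section 5.9 and footnote f stop at progression or new treatment.
- Section 5.10 takes the patient off study at progression, while footnote i keeps the patient in phone follow-up.
- Section 7.4 promises all pertinent safety observations, and 7.6.3.13 runs past progression.

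**Step 3. How much residual exposure lies outside the window?** Section 2.3.2 gives a terminal half-life of 20 to 40 hours. Taking five half-lives as washout (an assumed convention, not in the plan):

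- 5 × 20 h / 24 = 4.2 days
- 5 × 40 h / 24 = 8.3 days

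Scans are every 8 weeks, that is 56 days or two 28-day cycles. Dosing in the second cycle ends on day 28 + 21 = 49. If cycles run on time, a scheduled scan follows about 56 − 49 = 7 drug-free days. Progression found on such a scan leaves between none and about 1.3 days (8.3 − 7) of the assumed washout uncovered. Progression declared clinically, or on an off-schedule scan during a dosing week, can leave the whole 4.2 to 8.3 days uncovered. This concerns drug exposure only. An event can also appear after washout.

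**Step 4. What does one event weigh?** Section 13 plans 20 evaluable DTC patients, and section 1.1 allows up to 24. One patient's event, missed or wrongly counted, moves a frequency by 1/20 = 5.0 or 1/24 = 4.2 percentage points.

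**Step 5. Does the primary analysis change?** The DTC rule continues with at least 3 responses in 9 and succeeds with at least 8 in 20. Exact binomial calculation gives early stopping 0.601 and type I error 0.090 at a 25% response rate, and power 0.806 at 49%. The plan states 60%, 9% and 81%. None of these depends on adverse-event collection.

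**The case against.** The strongest reply is that footnote j sets only the routine frequency, and that 7.4, 7.6.3.8 and 7.6.3.13 already require wider capture. The end-of-treatment column schedules an examination, vital signs, laboratory tests, urinalysis and an EKG without regard to progression. Every event carries dates and an attribution, so late unrelated events can be separated at analysis. With one arm there is no between-group safety contrast to distort. Much of this stands, and it limits the size of the problem. It does not remove it: footnote j states an end point as well as a frequency, no other section gives a closing date for new non-fatal events, and attribution cannot restore events that were never sought.

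A reader might infer stronger versions, which the documents do not support:

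- **That patients are seen for toxicity only once a month.** Clinic visits fall on about days 1, 8, 15, 29 and 43, at intervals of 7, 7, 14 and 14 days. From cycle 3 there is one visit per 28-day cycle, which fits a monthly rule.
- **That toxicity behind the cycle 1 dose steps would go unrecorded.** Section 5.1 makes the first step conditional on toxicity ("the dose will be escalated to 120mg daily starting day8"), as it does the next. Visits coincide with these steps, and 7.4 requires start and stop dates and the action taken.
- **That progressing patients have no post-treatment capture at all.** The end-of-treatment visit, serious-event follow-up and the 30-day death rule give partial capture, and a scheduled scan usually follows an off week.
- **That other patients are observed for a further 24 months.** Footnote j has no such figure. It comes from other footnotes and runs from registration, so time after treatment is shorter.
- **That adverse-event frequencies are the only safety output.** Section 7.4 also names laboratory, vital-sign and ECG changes as safety variables.

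The calendar's adverse-event row cannot be read reliably in the text available, so the point rests on the footnote's wording.

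**Conclusion.** The point holds in a limited form. As written, routine collection closes on an efficacy outcome. Patients who stop for progression have no stated window for new non-fatal events, serious or not, beyond the end-of-treatment visit. Patients who stop for other reasons remain under assessment until progression, even on a new therapy. Section 13 pools these periods without saying so.

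The consequence is modest: a descriptive secondary objective in a small single-arm study, with one event worth roughly 4 to 5 percentage points in the DTC cohort. The direction is plausible (undercounting late related events in progressors, counting unrelated ones in the others), but the net bias cannot be calculated, because the documents give neither the expected split of stopping reasons nor late event rates. The exposure estimate rests on the assumed five-half-life convention and on cycles running to schedule. The change is worth making because it is cheap and replaces an outcome-dependent rule with a uniform one.

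**What to change.** 1. Reword footnote j so that adverse events are recorded at every scheduled clinic visit, including end of treatment, and through one fixed post-treatment window that is the same for every patient whatever the progression status. The 30-day figure already in 7.6.3.13 can be used. State the starting point: 7.6.3.13 counts from the end-of-treatment visit, whereas the monitoring text in 12.2 counts from the intervention. Counting from the last dose would give every patient the same length.
2. Add a sentence to section 13: adverse-event frequencies are summarised within that window, and later events, or events after a new cancer treatment begins, are listed separately.
3. Reconcile 5.9, 5.10 and footnotes f, i and j so that a patient who progresses remains available for this contact.
4. For the 8 MTC patients already enrolled, state in the report which collection rule applied.

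The cost is a footnote edit, one sentence in section 13 and at most one extra adverse-event contact, by phone, per progressing patient: no more than 24 contacts if all 24 possible DTC patients progress. No sample size, decision rule or treatment provision changes.

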11. MEASUREMENT OF EFFECT

11.1 Antitumor Effect – Solid Tumors

For the purposes of this study, participants should be re-evaluated for response every 8 weeks. In addition to a baseline scan, confirmatory scans should also be obtained 8 weeks following initial documentation of objective response.

Response and progression will be evaluated in this study using the new international criteria proposed by the Response Evaluation Criteria in Solid Tumors (RECIST) guideline (version 1.1) [Eur J Ca 45:228-247, 2009]. Changes in the largest diameter (unidimensional measurement) of the tumor lesions and the shortest diameter in the case of malignant lymph nodes are used in the RECIST criteria.

11.1.1 **Definitions**

Evaluable for Target Disease response. Only those participants who have measurable disease present at baseline, have received at least one cycle of therapy, and have had their disease re-evaluated will be considered evaluable for target disease response. These participants will have their response classified according to the definitions stated below. (Note: Participants who exhibit objective disease progression prior to the end of cycle 1 will also be considered evaluable.)

Evaluable Non-Target Disease Response. Participants who have lesions present at baseline that are evaluable but do not meet the definitions of measurable disease, have received at least one cycle of therapy, and have had their disease re-evaluated will be considered evaluable for non-target disease. The response assessment is based on the presence, absence, or unequivocal progression of the lesions.

11.1.2 **Disease Parameters**

Measurable disease. Measurable lesions are defined as those that can be accurately measured in at least one dimension (longest diameter to be recorded) as 2: 20 mm by chest x-ray or 2:10 mm with CT scan, MRI, or calipers by clinical exam. All tumor measurements must be recorded in millimeters (or decimal fractions of centimeters).

Note: Tumor lesions that are situated in a previously irradiated area might or might not be considered measurable.

Malignant lymph nodes. To be considered pathologically enlarged and measurable, a lymph node must be 2:15 mm in short axis when assessed by CT scan (CT scan slice thickness recommended to be no greater than 5 mm). At baseline and in follow-up, only the short axis will be measured and followed.

Non-measurable disease. All other lesions (or sites of disease), including small lesions (longest diameter <10 mm or pathological lymph nodes with 2:10 to <15 mm short axis), are considered non-measurable disease. Bone lesions, leptomeningeal disease, ascites, pleural/pericardial effusions, lymphangitis cutis/pulmonitis, inflammatory breast disease, abdominal masses (not followed by CT or MRI), and cystic

lesions are all considered non- measurable.

Note: Cystic lesions that meet the criteria for radiographically defined simple cysts should not be considered as malignant lesions (neither measurable nor non-measurable) since they are, by definition, simple cysts.

'Cystic lesions' thought to represent cystic metastases can be considered as measurable lesions, if they meet the definition of measurability described above. However, if non- cystic lesions are present in the same participant, these are preferred for selection as target lesions.

Target lesions. All measurable lesions up to a maximum of 2 lesions per organ and 5 lesions in total, representative of all involved organs, should be identified as **target lesions** and recorded and measured at baseline. Target lesions should be selected on the basis of their size (lesions with the longest diameter), be representative of all involved organs, but in addition should be those that lend themselves to reproducible repeated measurements. It may be the case that, on occasion, the largest lesion does not lend itself to reproducible measurement in which circumstance the next largest lesion which can be measured reproducibly should be selected. A sum of the diameters (longest for non-nodal lesions, short axis for nodal lesions) for all target lesions will be calculated and reported as the baseline sum diameters. If lymph nodes are to be included in the sum, then only the short axis is added into the sum. The baseline sum diameters will be used as reference to further characterize any objective tumor regression in the measurable dimension of the disease.

Non-target lesions. All other lesions (or sites of disease) including any measurable lesions over and above the 5 target lesions should be identified as **non-target lesions** and should also be recorded at baseline. Measurements of these lesions are not required, but the presence, absence, or in rare cases unequivocal progression of each should be noted throughout follow up.

